7. GENERAL CONSIDERATIONS

Derivation of the PK parameters for DPPC in serum will be the responsibility of the clinical pharmacokineticist at [REDACTED]. The PK and safety summaries and data listings as well as the statistical analysis of the PK variables will be the responsibility of the study biostatistician at [REDACTED].

Some minor modifications may be necessary to the planned design of tables, figures, and listings to accommodate data collected during the actual study conduct.

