2.2. SECONDARY OBJECTIVES

- To evaluate if any systemic exposure of dipalmitoylphosphatidylcholine (DPPC) can be detected in serum at levels higher than endogenous DPPC levels in serum in up to 15 healthy adult volunteers who will be evaluated in the Cohort B dose (OP0210 60 mg per day) versus placebo.
- To evaluate if any systemic exposure of cholestryl palmitate (CP) can be detected in serum at levels higher than endogenous CP levels in serum in up to 15 healthy adult volunteers who will be evaluated in the Cohort B dose (OP0210 60 mg per day) versus placebo (if feasible).

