7.1. SUMMARY STATISTICS

For qualitative or categorical variables, the population size (N for sample size and n for number of non-missing values) and the percentage (of available data) for each class of the variable will be presented. Quantitative variables, including PK variables (serum concentrations and PK parameters for DPPC) will be summarized using descriptive statistics, including N, n, mean, standard deviation (SD), coefficient of variation (CV%) as appropriate, median, minimum, and maximum values. Geometric mean (GMean) and geometric coefficient of variation (GCV%) will be included for PK parameters, where applicable. For t_{max} , only N, n, median, minimum, and maximum will be reported. Coefficient of variation will not be presented for change-from–baseline results. A minimum of 3 valid data values (n=3) is required for all descriptive statistics to be generated. If n is less than 3, only N, n, minimum, and maximum will be reported.

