7.3. PRECISION

Safety variables (i.e., otoscopy, tympanometry, nasal and epipharynx endoscopy, UPSIT olfactory test, audiology pure tone hearing test, clinical laboratory values, vital signs, and ECG intervals), including derivations thereof, will be reported to the same precision as the source data.

For all PK, and quantitative safety lab data, the precision of the descriptive statistics will be based upon the interpreted number of decimal places or significant figures (according to whichever precision method is applicable for that statistic) of the respective source dataset, defined as the precision of the non-excluded value with the most common precision in the entire source dataset (across all time points and treatment periods, within the subgroup as applicable).

All PK concentrations will be reported and analyzed with the same precision as the source data provided by the bioanalytical laboratory regardless of how many significant figures or decimal places the data carry. Elapsed time variables for PK will be analyzed and reported with 2 decimal places with units of hours. Pharmacokinetic parameters derived by the clinical pharmacokineticist will be considered equivalent to raw data and will be mapped to the CDISC SDTM (Clinical Data Interchange Standards Consortium Study Data Tabulation Model) database using Implementation Guide Version 3.2 without any rounding applied to parameter estimates. All PK parameters will be rounded for reporting purposes in CDISC ADaM (Analysis Dataset Model) datasets and in by-subject listings. The rounded PK parameter

data will be used for the calculation of descriptive statistics and in all statistical analyses. The precision for each PK parameter will be indicated by the clinical pharmacokineticist in the form Pharmacokinetic Review of WinNonlin Analysis (PI_FM_PK0203). Parameters directly derived from source data (e.g., C_{max}) will be analyzed and reported with the same precision as the source data. Actual elapsed sample collection times and parameters derived from them (e.g., t_{max}) will be reported to 2 decimal places with units of hours.

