For the reporting of descriptive statistics of Safety, and PK data, the arithmetic mean, GMean (for PK parameters only), SD, median, and confidence intervals (CIs) will be presented to 1 decimal place or significant figure more than the precision of the source data, according to whichever precision method is applicable to the source data provided by the study database, safety laboratory, or bioanalytical laboratory regardless of how many significant figures or decimal places the data carry. The minimum and maximum will be presented to the same decimal place or significant figure precision as the source data, according to whichever precision method is applicable to the source data. All the above statistics for PK concentrations and C_{max} will have precision based on the same precision method interpreted to have been used in the source data. Coefficient of variation, GCV%, and other percentages will always be reported to 1 decimal place.

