16. PHARMACOKINETIC ANALYSIS

16.1. SERUM CONCENTRATION DATA

Subjects with partial data will be evaluated on a case-by-case basis to determine if sufficient data are available for reliable estimation of PK parameters. If a subject is missing both predose sample collections, their observed concentrations will be listed and summarized but not included in baseline-corrected listings or summaries.

A listing of PK blood sample collection times as well as derived sampling time deviations will be provided. Baseline-corrected DPPC serum levels will be derived by subtracting the observed levels at sample time on Day 14 from the mean baseline on Day 1 predose, if possible. If the resulting value is negative, the estimated baseline-corrected level will be set to zero (0) for purposes of reporting and subsequent analysis.

Observed and baseline-corrected serum concentrations will be summarized by treatment using

Document: Statistical Analysis Plan
Author: [REDACTED]

Version Number:
Version Date:

2.0
03APR2019

descriptive statistics. Predose and postdose concentrations of DPPC that are below the limit of quantification (BLQ) will be treated as zero for the computation of descriptive statistics.

A subject listing of all observed and baseline-corrected concentration-time data will be presented by treatment. Figures of arithmetic mean of observed and baseline-corrected concentration-time data (\pm SD, as appropriate) will be presented by treatment on linear and semi-logarithmic scales. Individual subject observed concentration-time data will be graphically presented on linear and semi-logarithmic scales.

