16.2. PHARMACOKINETIC PARAMETERS

For PK parameter calculations, if both Day 1 predose samples are missing, no PK parameters will be estimated for this subject. If any predose sample is BLQ, it will be assigned a numerical value of zero for PK parameter calculations and baseline calculations.

Any other BLQ concentrations will be assigned a value of zero if they precede quantifiable samples in the initial portion of the profile on Day 14. A BLQ value that occurs between quantifiable data points, especially prior to C_{max} , will be evaluated to determine if an assigned concentration of zero makes sense, or if exclusion of the data is warranted. Following C_{max} , BLQ values embedded between 2 quantifiable data points will be treated as zero when calculating PK parameters. If a BLQ value occurs at the end of the collection interval (after the last quantifiable concentration), it will be set to zero.

The following PK parameters will be estimated for serum DPPC by non-compartmental methods using actual elapsed time from dosing.

C_{max}	Maximum baseline-corrected serum concentration (μ g/mL) obtained directly from the baseline-concentration versus time data.
t_{max}	Time of maximum baseline-corrected serum concentration (h), obtained directly from the observed baseline-concentration versus time data.

A subject listing of individual PK parameters will be provided. Pharmacokinetic parameters will be summarized by treatment using descriptive statistics.

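### The DPPC objective is a comparison with placebo, but the SAP plans only by-treatment summaries of floored values and C_max, with no signed change, no between-group difference and no interval

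*SAP*

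**What the plan says.** SAP 2.2 asks whether systemic DPPC "can be detected in serum at levels higher than endogenous DPPC levels in serum in up to 15 healthy adult volunteers", at the "Cohort B dose (OP0210 60 mg per day) versus placebo". The protocol synopsis labels this objective secondary/exploratory. SAP 4.3 drops the analysis of CP because its assay is not feasible, so DPPC is the only secondary analysis left.

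The planned handling is descriptive:
- SAP 16.1: "Observed and baseline-corrected serum concentrations will be summarized by treatment using" descriptive statistics. Negative corrected values are set to zero.
- SAP 16.2: C_max and t_max come from the corrected profile. "Pharmacokinetic parameters will be summarized by treatment using descriptive statistics".
- SAP 7.1: PK variables "will be summarized using descriptive statistics, including N, n, mean, standard deviation (SD), coefficient of variation (CV%) as appropriate, median, minimum, and maximum values", with geometric mean and geometric CV added for parameters. The list contains no difference, ratio or interval.

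Two sentences use wider language. SAP 7 gives the summaries and listings "as well as the statistical analysis of the PK variables will be the responsibility of the study biostatistician". SAP 7.3 says the rounded PK parameter "data will be used for the calculation of descriptive statistics and in all statistical analyses". SAP 7.3 also has a decimal-place rule shared by safety and PK data: "SD, median, and confidence intervals (CIs) will be presented to 1 decimal place or significant figure more than the precision of the source data".

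On placebo samples the documents differ. Protocol 8.5.2 has placebo baseline samples assayed to establish the endogenous level and placebo post-dose samples left unassayed. The protocol's PK analysis set (9.3) is limited to OP0201 recipients. SAP 6.3 includes placebo subjects who have a quantifiable post-dose value. SAP 4.3 lists only the CP changes.

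**The concern.** The objective compares two groups, but nothing planned estimates that comparison or its uncertainty. The summaries that are planned cannot stand in for it. A corrected value floored at zero cannot average below zero, and a maximum over several samples tends upward from noise alone. A positive mean C_max on OP0201 is therefore expected whether or not any DPPC is absorbed. In the other direction, similar columns for 12 and 3 subjects could be read as absence of exposure when three placebo subjects leave a large rise unexcluded. With no prespecified estimate, either reading could be chosen after unblinding.

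**Working it through.** **Inputs.** Cohort B has 15 subjects randomised 4:1 (SAP 8.1). Baseline is the mean of two Day 1 predose samples (SAP 7.5). Day 14 post-dose samples are at 5, 20, 35 and 50 minutes (schedule footnote s). Negatives are set to zero (SAP 16.1). The documents give no SD, alpha, power or effect size, so results are in SD units and the error model is an assumption.

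**1. Allocation.** 15 × 4/5 = 12 and 15 × 1/5 = 3, matching SAP Table 1. There is no other planning figure to reproduce.

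**2. The planned statistic with no exposure.** Let each sample be the subject's own level plus independent normal error with within-subject SD w. Let B be the mean of the two predose samples, and C_max = max(0, largest of four post-dose values − B). Simulating 1,000,000 subjects gives:
- P(C_max > 0) = 0.851, mean 1.103 w, SD 0.877 w.
- If the Day 14 predose sample is counted as well: 0.886 and 1.214 w.
- For a single floored time point: mean 0.487 w.

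Read literally, SAP 16.1 subtracts observed from baseline. With that sign the no-exposure result is the same by symmetry (0.850 and 1.103 w).

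**3. An interval around C_max would not repair this.** With n = 12 the half-width is 2.201 × 0.877 w / √12 = 0.557 w. Around 1.103 w that runs from about 0.55 w to 1.66 w, above zero although exposure is nil.

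**4. A signed change.** For each subject, take the mean of the four Day 14 post-dose values minus the mean of the two Day 1 predose values, unfloored. With no exposure its expectation is zero. Let s be its between-subject SD (not given).
- OP0201 mean, n = 12: 2.201 / √12 = 0.635 s.
- OP0201 minus placebo, 12 v 3: 2.160 × √(1/12 + 1/3) = 2.160 × 0.6455 = 1.394 s.
- With one placebo subject lost: 2.179 × √(1/12 + 1/2) = 1.66 s. SAP 7.1 would then also suppress the placebo mean and SD, because n is below 3.
- An 80% chance that the 95% interval excludes zero needs a true difference of about 1.96 s, against 0.89 s for the within-group change.
- As a ratio of geometric means, the 12 v 3 interval is the estimate divided and multiplied by 1.32, 1.51 or 1.93 at an assumed between-subject CV of 20%, 30% or 50%.

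**5. Is the difference computable?** Under protocol 8.5.2 no placebo Day 14 post-dose values exist. Under SAP 6.3 they must exist, since a quantifiable post-dose value is a condition of entry to the PK set. Both cannot hold, and SAP 4.3 does not settle it. The 1.394 s figure applies only if the samples are assayed.

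**The case against.** Descriptive analysis is the declared design. Protocol 9.1 states no hypotheses, the sample size has no statistical basis, protocol 9.4.2 plans only summaries, and the objective is labelled exploratory. Each subject's own baseline is already the endogenous reference, so some comparison is planned. Individual listings for 15 subjects would let a reader work out an interval. A four-sample average could dilute a brief peak. The table shells mentioned in SAP 9 are not in the available text. All of this stands. It argues for an estimate alongside C_max and t_max rather than in place of them, and against a test. It does not make floored summaries informative about exposure.

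Three stronger readings are tempting but not supported:
- A reader might infer that the SAP promises a PK test or PK confidence interval and then omits it. The SAP 7 sentence allocates responsibilities. The SAP 7.3 interval wording is a rounding rule shared with safety data, where SAP 17.2 to 17.6 do plan 95% CIs. Loose wording explains both.
- A reader might infer a false-detection rate from chance alone: with no exposure, the OP0201 mean lies above zero in 50% of trials, and above both zero and the placebo mean in 1/4 + arcsin(√0.2)/(2π) = 32%. Those rates describe signed means and a reading rule that neither document states, not the planned floored statistic.
- A reader might infer that exposure should be declared only if the lower limit of the difference exceeds zero. With 12 v 3 and no hypotheses, such a rule would usually miss true rises well below 1.96 s. The documents do not call for it.

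**Conclusion.** The point holds as a gap in estimation. The SAP does not quantify the comparison that its own objective names, and what it does summarise is positive in about 85% of subjects, with a mean near 1.1 within-subject SD, when there is no exposure. Those two figures rest on independent normal errors, four post-dose samples and correction as observed minus baseline. The half-widths of 0.64 and 1.39 SD rest on full Cohort B enrolment, and the second also on placebo post-dose samples being assayed. The missing item is a signed between-group estimate with an interval. The absence of a powered test is not a defect here, and neither document says that a positive mean would be reported as exposure.

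**What to change.** 1. Reconcile protocol 8.5.2 with SAP 6.3 on whether placebo post-dose samples are assayed, and record any change in SAP 4.3.
2. Keep C_max and t_max as the named endpoints. Add to SAP 16 a supportive estimate for each Cohort B subject: mean Day 14 post-dose DPPC minus mean Day 1 predose DPPC, signed and not floored. Report the OP0201 mean change with its 95% CI.
3. If placebo post-dose samples are assayed, also report the OP0201-minus-placebo difference with its 95% CI. If they are not, state that no conclusion against placebo will be drawn.
4. Present the result as estimation without a pass/fail rule, and state that a wide interval including zero does not support a claim of no systemic exposure.
5. Define the statistical-analysis wording in SAP 7 and 7.3 by pointing to this estimate, or remove it.

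The cost is a short SAP paragraph, one extra table and possibly the assay of placebo samples already collected. The resulting claim will be less favourable because the interval is wide.

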7.1. SUMMARY STATISTICS

For qualitative or categorical variables, the population size (N for sample size and n for number of non-missing values) and the percentage (of available data) for each class of the variable will be presented. Quantitative variables, including PK variables (serum concentrations and PK parameters for DPPC) will be summarized using descriptive statistics, including N, n, mean, standard deviation (SD), coefficient of variation (CV%) as appropriate, median, minimum, and maximum values. Geometric mean (GMean) and geometric coefficient of variation (GCV%) will be included for PK parameters, where applicable. For t_{max} , only N, n, median, minimum, and maximum will be reported. Coefficient of variation will not be presented for change-from–baseline results. A minimum of 3 valid data values (n=3) is required for all descriptive statistics to be generated. If n is less than 3, only N, n, minimum, and maximum will be reported.

7.2. TREATMENT SUMMARIZATION

In general, unless otherwise stated for specific endpoints in the respective sections of this document, data will be presented for each treatment group, with placebo subjects from both cohorts combined into a single, overall placebo group. Data for all active treated subjects and for all treated subjects combined will also be presented when appropriate.

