4.2 Scientific Rationale for Study Design

This study is designed to evaluate the safety and tolerability of OP0201 versus placebo in healthy volunteers using a well-designed, scientific method for comparing treatments.

The study design is that of a well-controlled clinical study that includes elements necessary for a valid evaluation of safety and tolerability of repeat OP0201 doses for 14 days. The study is randomized, and treatment is masked for the Investigator, study center personnel, and the subjects to minimize bias. A parallel-group design eliminates possible confounding effects that are inherent in other study designs (eg, cross over).

The placebo (HFA-134a minus active ingredients) was selected to evaluate the comparative safety profile of OP0201 versus a non-drug containing control arm. HFA-134a was chosen as the placebo control since it is the propellant used in the OP0201 formulation. HFA-134a is used as a propellant in other marketed nasal products and has a good safety and tolerability profile in patients suffering from perennial allergic rhinitis ([Weber et al, 2006](#)).

The current study is designed to show that OP0201 is safe and well tolerated compared to the placebo ([FDA Drug Study Designs - Information Sheet](#)).

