6.1 Study Treatment(s) Administered

The following study treatments will be used in this study.

Study Treatment #1: OP0201

OP0201 is an intranasal aerosol, a dosage form recognized by the US Pharmacopeia, that is comprised of 2 active ingredients, DPPC and CP, in approximately 20:1 (w/w) ratio, suspended in an inactive ingredient, the synthetic chlorofluorocarbon-free propellant HFA 134a. All OP0201 ingredients are synthetic; none of these ingredients contain any animal or human derivatives. OP0201 is supplied in mechanical packing parts that includes a pressurized canister with a securely attached metering valve where the drug product is contained, an actuator into which the canister is seated and the valve connects with device body, and a tip to deliver the drug to the nostrils.

OP0201 is manufactured using Good Manufacturing Processes (GMP) with development phase appropriate compliance with global Health Authority guidelines (eg, [US FDA Guidance for Industry: Nasal Spray and Inhalation Solution, Suspension and Spray Drug Products, July 2002](#)) by [REDACTED]. The OP0201 canisters are filled to deliver 100 actuations (sprays) per canister. Each MDI spray of OP0201 delivers 0.1 mL of HFA-134a containing a total of 2.5 mg of the active pharmaceutical ingredients as dry powder suspended in the HFA-134a.

See the IB for further details regarding OP0201.

Study Treatment #2: Placebo

The placebo is comprised of the same synthetic chlorofluorocarbon-free propellant, HFA-134a, an inactive ingredient as used in the study treatment #1 described above. The placebo is manufactured using GMP with development phase appropriate compliance with global Health Authority guidelines (eg, [US FDA Guidance for Industry: Nasal Spray and Inhalation Solution, Suspension and Spray Drug Products, July 2002](#)) by [REDACTED].

The placebo canisters are filled to deliver 100 actuations (sprays) per canister. Each 0.1 mL MDI spray of placebo delivers 0.1 mL of HFA-134a.

For each dose, the subject will have administered to them by the study center staff, 2 (Cohort A) or 4 (Cohort B) consecutive sprays first to the left nostril and then to the right nostril for a total of 4 (Cohort A) or 8 (Cohort B) sprays (see Study Manual for Study Treatment Instructions for Use). The dose will be repeated 3 times a day for a total of 14 days (42 doses).

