All AE tabulations will be performed by treatment and with all active treated subjects combined overall as well as all placebo treated subjects combined from both cohorts displaying the number and percentage of subjects. Incidence of TEAEs will be tabulated as follows:

- Across System Organ Class (SOC) and Preferred Term (PT): serious TEAEs and those leading to death or study discontinuation, related TEAEs and serious related TEAEs, by severity, and related TEAEs by severity.
- By System Organ Class (SOC) and Preferred Term (PT).

- By System Organ Class (SOC), Preferred Term (PT) for TEAEs related to study medication.
- By System Organ Class (SOC), Preferred Term (PT) and maximum severity.
- By System Organ Class (SOC), Preferred Term (PT) and maximum severity for TEAEs related to study medication.

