APPENDIX 1. PROGRAMMING CONVENTIONS FOR OUTPUTS

This appendix (including the example layout) is optional, depending on the customer. Include if no customer guidelines, otherwise reference customer guidelines

OUTPUT CONVENTIONS

Outputs will be presented according to the [REDACTED] Global Biostatistics Standard Output Conventions, which is available upon request.

DATES & TIMES

Depending on data available, dates and times will take the format yyyy-mm-dd; times will take the format hh:mm:ss; combined dates and times will take the format yyyy-mm-ddThh:mm:ss.

SPELLING FORMAT

English US

PRESENTATION OF TREATMENT GROUPS

For most safety outputs, data will be summarized by treatment groups and will be represented as follows and in that order:

Treatment Group	For Tables
OP0201 30 mg	OP0201 30 mg administered intranasally (2 sprays per nostril) TID for 14 consecutive days
OP0201 60 mg	OP0201 60 mg administered intranasally (4 sprays per nostril) TID for 14 consecutive days
All Active	All Active Treated Subjects
All Placebo	All Placebo Treated Subjects
All Subjects	All Treated Subjects

Some safety outputs will summarize data by cohorts and treatment groups, they will be represented as follows and in that order:

Treatment Group	For Tables
Cohort A, Overall	OP0201 30 mg or Placebo administered intranasally (2 sprays per nostril) TID for 14 consecutive days
Cohort A, OP0201 30 mg	OP0201 30 mg administered intranasally (2 sprays per nostril) TID for 14 consecutive days

Document: Statistical Analysis Plan

Author: [REDACTED]

Version Number:

2.0

Version Date:

03APR2019

Treatment Group	For Tables
Cohort A, Placebo	Placebo administered intranasally (2 sprays per nostril) TID for 14 consecutive days
Cohort B, Overall	OP0201 60 mg or Placebo administered intranasally (4 sprays per nostril) TID for 14 consecutive days
Cohort B, OP0201 60 mg	OP0201 60 mg administered intranasally (4 sprays per nostril) TID for 14 consecutive days
Cohort B, Placebo	Placebo administered intranasally (4 sprays per nostril) TID for 14 consecutive days
All Active	All Active Treated Subjects
All Placebo	All Placebo Treated Subjects
All Subjects	All Treated Subjects

PRESENTATION OF VISITS

For safety outputs, except those related to AEs, visits will be represented as follows and in that order:

Treatment Period	Visit Name(s)
Screening Day -28 to -1	Screening
Confinement Period	Day -1, Day 1, Day 4, Day 8, Day 14, Day 15
Study Exit	ET, Day 21 Follow-up

ET=Early Termination

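### Most safety tables set both OP0201 doses against one placebo column that averages 12 and 24 propellant sprays a day, so neither dose is shown beside its own spray-matched, concurrent placebo

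*SAP*

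**What the plan says.** SAP 7.2 sets the default: unless a section states otherwise, data are shown per treatment group, "with placebo subjects from both cohorts combined into a single, overall placebo group". SAP 17.1 has adverse event tables by treatment, with all active subjects combined, "as well as all placebo treated subjects combined from both cohorts displaying the number and percentage of subjects". SAP 17.2, 17.3, 17.4 and 17.6 (otoscopy, tympanometry, endoscopy, audiology) tabulate by treatment, and 17.5 (UPSIT) names no grouping, so the default applies to them.

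SAP Appendix 1 gives two column layouts. The first begins "For most safety outputs, data will be summarized by treatment groups" and has OP0201 30 mg, OP0201 60 mg, All Active, All Placebo and All Subjects. The second begins "Some safety outputs will summarize data by cohorts and treatment groups" and adds separate columns for Cohort A placebo ("Placebo administered intranasally (2 sprays per nostril) TID for 14 consecutive days") and Cohort B placebo ("Placebo administered intranasally (4 sprays per nostril) TID for 14 consecutive days"). The appendix does not say which outputs use it. Section 10 tabulates disposition by cohort and treatment; no section from 17.1 to 17.6 does the same.

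On the placebo, Protocol 4.2 explains that "HFA-134a was chosen as the placebo control since it is the propellant used in the OP0201 formulation", and Protocol 6.1 has staff give "2 (Cohort A) or 4 (Cohort B) consecutive sprays first to the left nostril" and then the same to the right. Randomisation is 4:1 within each cohort, and Cohort B follows a safety review held after Cohort A completes Day 14 (Protocol 4.1 and 4.5). Neither document mentions the unequal propellant exposure or gives a reason for pooling.

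**The concern.** A propellant-only placebo isolates the active ingredients when both arms receive the same number of sprays. That is true within a cohort but not against the pool. The 30 mg group (12 sprays a day) and the 60 mg group (24) are both read against a column that averages 18. Because the cohorts are sequential, any difference between the two periods enters the contrasts in the same way.

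The outcomes at stake are mainly the local ones: nasal adverse events, endoscopy, otoscopy, tympanometry and smell. For these, spray volume could be a cause in its own right. A reader could take a spray or period effect for a drug effect at 60 mg, or could miss a real effect at 30 mg because the comparator received 50% more sprays on average (18/12 = 1.5). PK is unaffected, since it uses Cohort B only.

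**Working it through.** **Exposure, reproducing the SAP's figures.** Sprays per subject = sprays per nostril × 2 nostrils × 3 doses × 14 days.
- Cohort A: 2 × 2 × 3 × 14 = 168, or 12 a day.
- Cohort B: 4 × 2 × 3 × 14 = 336, or 24 a day.

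Both match SAP 15. At 0.1 mL of propellant per spray (Protocol 6.1), this is 1.2 and 2.4 mL a day, exactly two-fold. Allocation is 15 × 4/5 = 12 OP0201 and 15 × 1/5 = 3 placebo per cohort, so pooled placebo has 6 subjects averaging (3 × 12 + 3 × 24)/6 = 18 sprays a day.

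**Bias when the active ingredients have no effect.** Let pA and pB be the event rates in Cohorts A and B, the same in both arms of a cohort.
- Pooled placebo = (3pA + 3pB)/6 = (pA + pB)/2.
- 30 mg minus pooled placebo = −(pB − pA)/2.
- 60 mg minus pooled placebo = +(pB − pA)/2.
- All Active minus All Placebo = (12pA + 12pB)/24 − (pA + pB)/2 = 0.
- Within each cohort, OP0201 minus placebo = 0.

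**Precision.** The root mean squared error (RMSE) of OP0201 minus placebo in a cohort with rate p is:
- split: √[p(1−p)(1/12 + 1/3)]
- pooled: √[p(1−p)/12 + {3pA(1−pA) + 3pB(1−pB)}/36 + ((pB−pA)/2)²]

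Example, 30 mg at 10%/20%: split √(0.0075 + 0.0300) = 19.4 points; pooled √(0.0075 + 0.0208 + 0.0025) = 17.6 points.

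The documents give no event rates, so the pairs below are assumptions. All differences and errors are in percentage points.

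| pA / pB | Pooled placebo | 30 mg − pool | 60 mg − pool | 60 mg − 30 mg | RMSE 30 mg, split / pooled | RMSE 60 mg, split / pooled |
|---|---|---|---|---|---|---|
| 10% / 20% | 15% | −5 | +5 | +10 | 19.4 / 17.6 | 25.8 / 19.1 |
| 20% / 40% | 30% | −10 | +10 | +20 | 25.8 / 23.8 | 31.6 / 25.2 |
| 30% / 60% | 45% | −15 | +15 | +30 | 29.6 / 27.8 | 31.6 / 28.3 |
| 40% / 80% | 60% | −20 | +20 | +40 | 31.6 / 30.6 | 25.8 / 29.4 |

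The 60 mg minus 30 mg column contains no placebo term, so it is the same whether placebo is pooled or split.

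**What 3 subjects can show.** The exact 95% interval for 0/3 runs from 0 to 1 − 0.025^(1/3) = 70.8%. Even 3/3 against 0/3 gives a two-sided Fisher p of 0.10. Under SAP 7.1, descriptive statistics need 3 values, so for a quantitative variable one missing value reduces a cohort placebo column to N, n, minimum and maximum.

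**The case against.** Five arguments favour leaving the plan alone.

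1. **By-cohort columns already exist.** Appendix 1 defines them. SAP 9 says the table shells set format and content, and the shells are not in the public text; they may name the outputs concerned. Listings are ordered by cohort, so each placebo subject can be traced. This stands in part: the SAP's own text still leaves the choice open for the primary-endpoint tables.

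2. **SAP 17.1 may not mean pooled placebo only.** A reader might infer that it fixes pooling for every adverse event table. Its wording can equally be read as adding combined columns to others, as Section 10 does. The text is ambiguous and does not support the firmer reading.

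3. **The safety analysis is descriptive.** SAP 17 plans no statistical comparisons between groups. That is true, but the primary objective is safety and tolerability relative to placebo, and these tables are the evidence for it.

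4. **Pooling buys precision.** This stands. At three of the four assumed pairs pooled placebo has the smaller error for both doses; at 40%/80% it loses for 60 mg. A reader might infer that conclusions about the active ingredients should rest only on the within-cohort contrast. With 3 placebo subjects per cohort, the calculation does not support that.

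5. **A propellant effect may be small.** Protocol 4.2 describes HFA-134a as well tolerated nasally, and Protocol 5.2 excludes current or recent respiratory infection and allergy, which limits period effects. This bears on the likely size of the bias, not on its direction.

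**Conclusion.** The default presentation omits the comparator that the design provides for each dose: a placebo group with the same spray count, randomised in the same cohort and period. Under a pure spray or period effect, the dose-versus-placebo differences are biased by −(pB − pA)/2 at 30 mg and +(pB − pA)/2 at 60 mg, or 5 to 20 points each way over the assumed range. All Active against All Placebo is unbiased. These results assume the planned 12:3 allocation, full dosing and rates that are not in the documents; if the cohort rates are equal, there is no bias.

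A reader might infer that pooling manufactures a dose-response. It does not. The 60 mg versus 30 mg gap comes from the cohort design and would remain with split columns. The expected pattern is 30 mg below pooled placebo and 60 mg above it. What pooling removes is the matched reference needed to interpret the gap. Showing that reference makes the tables interpretable, but 3 subjects per cohort cannot settle whether the propellant has an effect.

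**What to change.** In SAP 7.2 and 17.1 to 17.6, name the adverse event, otoscopy, tympanometry, nasal and epipharynx endoscopy, UPSIT and audiology tables as using the existing Appendix 1 cohort-by-treatment layout, with Cohort A placebo and Cohort B placebo in separate columns. Keep All Placebo alongside. In 17.1, make clear that the combined columns are additional.

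Add a short statement that:
- pooled placebo averages two propellant exposures and two periods;
- each dose should be read against both its own-cohort placebo and the pooled placebo;
- with 3 subjects per cohort placebo, the tables cannot establish or exclude a propellant effect, and one missing value triggers the SAP 7.1 rule for fewer than 3 values.

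The cost is SAP and shell wording plus two more placebo columns per table. No new data, subjects or methods are needed. The change should be made before treatment is unblinded for the final analysis (SAP 5.3), so that the comparator is not chosen with results in view.
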